3.2.5.2.6 The time to the minimal score post dose

This will be calculated for sub-scales ANS, AAS and ATS as the difference (in mins) between the actual time when the minimal number is observed and the time of receiving glucagon. Actual Time will be used to the calculation of the following variables.

- Subjects who never develop symptoms will be assumed to have a value of 0.

This parameter will be analyzed both on time from receiving glucagon and from a decision to dose.

3.2.5.2.7 The time to first reporting of “no” for the global hypoglycemia question will be defined as below:

This will be calculated as the difference (in mins) between the actual time when the first “no” for “Overall Assessment of Hypoglycemia” is observed and the time receiving glucagon. Actual Time will be used to the calculation of the following variables.

- Subjects who never develop symptoms (never answers No) will be assumed to have a value of 0.
- In very rare cases, if subject answers Yes all the way to the last time point, the total time will be recorded. (And it will be analyzed based survival model.)

This parameter will be analyzed both on time from receiving glucagon and from a decision to dose.

3.2.5.2.8 The Glucagon Preparation Time:

Glucagon preparation time (min) is defined as the time between “decision to dose” and time of study drug administration to the abdomen. Actual Time will be used to calculate this variable.

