2 INVESTIGATIONAL PLAN

2.1 STUDY DESIGN AND RANDOMIZATION

2.1.1 Study Design

This is a non-inferiority, multi-centered, randomized, controlled, single-blind, two-way crossover efficacy and safety in-patient study in subjects with Type 1 diabetes mellitus (T1D).

Table 2-1: Randomized treatment sequence

Group	Dose 1	Dose 2
1	G-Pen™ 1 mg	Lilly 1 mg
2	Lilly 1 mg	G-Pen™ 1 mg

The procedure consists of:

1. Inducing hypoglycemia by IV administration of regular insulin diluted in normal saline until the subjects reach a verified stable hypoglycemic state.
2. Treating subcutaneously with either 1 mg Lilly Glucagon or 1 mg G-Pen™ (glucagon injection).

Blood glucose levels will be monitored for up to 180 minutes post-dosing. Subjects will also complete a questionnaire about symptoms of hypoglycemia during the hypoglycemia induction phase and for up to 180 minutes after treatment with glucagon.

The specific hypoglycemia induction procedures and justification, and rules for interruption and termination of dosing are listed in the protocol.

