3.2.2 General guideline for define the protocol time

Protocol time is needed to find the 30-minute glucose value as well as to generate some of the glucose or hypoglycemia score curves.

Protocol time will be developed based on the following procedures:

- Protocol time zero will be based on either receiving glucagon or decision to dose:

- Receiving glucagon: T0 = actual time stamp of glucagon injection
- Decision to dose: T0 = actual time stamp when dose decision is made
- Subsequent protocol times are calculated by the following minutes plus T0:
 - 5, 10,15,20,25,30,35,40,45,50,55,60,65,70,75,80,85,90
 - 120,150,180
- For any continuous (number) variable, the value at the protocol time will be determined by linear interpolation between the two adjacent time points.
- For any categorical (text) variable, the value at the protocol time will be determined using the nearest value:
 - Protocol time 5 – 85 : -2 minute to +3 minute
 - Protocol time 90: -2 minute to 15 minute
 - Protocol time 120, 150, 180: -15 minute to +15 minute
 - If multiple values are attributed to a single protocol time, then the last value will be used

Many analyses will be done using both the protocol time based on receiving glucagon and the one based on decision to dose. These analyses will be noted in each of the corresponding sections.

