3.2.5.2.4 Hypoglycemia Symptom Mean Scores

Symptoms of hypoglycemia are captured using the following questionnaire:

Neuroglycopenic Symptoms	Severity Score (1-6)
Dizziness	
Blurred vision	
Difficulty in thinking	
Faintness	
Autonomic Symptoms	Severity Score (1-6)
Sweating	

Neuroglycopenic Symptoms	Severity Score (1-6)
Tremor	
Palpitations	
Feeling of nervousness	
Overall Assessment of Hypoglycemia	Yes/No
Do you currently feel hypoglycemic?	

The following 3 Mean Scores will be calculated for each subject at each of the measurement time points:

1. Average Neuroglycopenic Symptom Score (ANS) :

$$\frac{\text{Dizziness} + \text{Blurred vision} + \text{Difficulty in thinking} + \text{Faintness}}{4}$$

2. Average Autonomic Symptom Score (AAS):

$$\frac{\text{Sweating} + \text{Tremor} + \text{Palpitations} + \text{Feeling of nervousness}}{4}$$

3. Average Total Symptom Score (ATS):

$$\frac{\text{Sum of all symptoms}}{8}$$

Overall Assessment of Hypoglycemia:

- This will be treated as a categorical variable, so no means will be calculated.

This parameter will be analyzed both on time from receiving glucagon and from a decision to dose.

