3.3 STATISTICAL METHODS

3.3.1 General guideline for descriptive summaries

For continuous variables, mean, standard deviation, minimum, and maximum will be presented for each treatment group.

For categorical variables, count and % of subjects/counts in each treatment group will be presented.

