3.3.3.2.7 The time to first reporting of “no” for the global hypoglycemia question

The time to first reporting of “no” for the global hypoglycemia question will be summarized descriptively for each treatment. In rare cases if a subject does not answer “no,” the total time of 180 minutes will be used in the summary, but noted in the footnote.

A survival analysis will be done to compare the difference between treatment groups. P-value for the difference will be reported. Again, if a subject does not answer “no,” the total time of 180 minutes will be used, but noted as a censored value in the analysis model.

This will be done for ITT population only, and will be done with time based on both “receiving glucagon” and “decision to dose”.

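### SAP 3.2.5.2.7: the parenthesis in the zero-minute rule has Yes and No reversed, so it describes unrelieved subjects instead of symptom-free ones

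*SAP*

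**What the plan says.** The global item in SAP section 3.2.5.2.4 is a Yes/No question: "Do you currently feel hypoglycemic". Section 3.2.5.2.7 derives the time from receiving glucagon to the first No, in actual minutes, and adds two special rules.

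- First bullet: "Subjects who never develop symptoms (never answers No) will be assumed to have a value of 0".
- Second bullet, for subjects who are never relieved: "if subject answers Yes all the way to the last time point, the total time will be recorded". It adds that these cases go into a survival model and are expected to be very rare.

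Section 3.3.3.2.7 covers the analysis. In the descriptive summary a subject without a No is given 180 minutes, with a footnote. In the survival comparison, "the total time of 180 minutes will be used, but noted as a censored value in the analysis model". A p-value is planned, in the ITT population, on both the receiving-glucagon and the decision-to-dose clocks.

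The preceding endpoint, time to minimal score in section 3.2.5.2.6, has the same zero rule without any parenthesis: "Subjects who never develop symptoms will be assumed to have a value of 0".

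**The concern.** A No on this item means that the subject does not feel hypoglycemic. Someone without symptoms answers No every time. Someone who never answers No feels hypoglycemic at every assessment. The lead words of the first bullet and its parenthesis therefore describe opposite groups, and the bullet assigns 0 minutes without resolving which is meant.

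This sits in an operative derivation rule, not in background text. The parenthesis is also the only part of the bullet expressed in the Yes/No answers, so it is the part most easily turned into code. If that happened, treatment non-response would enter a secondary comparison as the best possible response, and the bias would favour whichever treatment left more subjects unrelieved.

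**Working it through.** The SAP gives no figure to reproduce here. The check is to map each answer pattern to the value that each rule assigns.

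| Answers after dosing | Lead words, first bullet | Parenthesis, first bullet | Second bullet | 3.3.3.2.7 |
|---|---|---|---|---|
| No throughout | 0 min | not met | does not apply | does not apply |
| Yes, then No | not met | not met | does not apply | does not apply |
| Yes throughout | not met | 0 min | total time | 180 min, censored |

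1. **Yes throughout.** The parenthesis gives an event at 0 minutes; the second bullet and 3.3.3.2.7 give a censored time at the end of follow-up. These are opposite ends of the 0 to 180 minute scale.
2. **No throughout.** This subject fits the lead words but fails the parenthesis. If only the parenthesis were coded, the subject would get the time of the first No after dosing instead of 0.
3. **Yes, then No.** No conflict: the value is the time of the first No minus time zero.

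**Size under literal coding.** Section 3.3.1 says "For continuous variables, mean, standard deviation, minimum, and maximum will be presented for each treatment group", so the mean is a reported quantity. Inputs: 180 minutes from 3.3.3.2.7, and N = 85 randomized subjects from 2.1.2, assumed observed on both treatments. The SAP gives no count k of unrelieved subjects, so I take 0 to 2.

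Shift in one treatment's mean = k × (180 − 0)/N.

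- k = 0: no effect.
- k = 1: 180/85 = 2.1 min lower.
- k = 2: 360/85 = 4.2 min lower.
- One on each treatment: both means fall by 2.1 min, and their difference is unchanged.

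Section 2.1.2 allows up to 5% missing observations. With 85 × 0.95 = 80.75, about 81 subjects, k = 1 gives 180/81 = 2.2 min, so the result hardly depends on N.

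**After correction.** With Yes in place of No in the parenthesis, each pattern has one handling: No throughout gives 0; Yes then No gives the observed time; Yes throughout gives 180 minutes, censored.

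**The case against.** The strongest reply is that the intended handling is plain. The lead words govern the bullet and exclude anyone who feels hypoglycemic throughout. The second bullet names those subjects and sends them to a survival model. Section 3.3.3.2.7 states their handling twice, once for the summary and once for the model. Section 3.2.5.2.6 has the same zero rule without the parenthesis. A programmer would have to ignore all of this to code unrelieved subjects as 0. That stands, and it is why the point is a wording error with a conditional consequence. A reader might infer that the SAP has chosen to score non-relief as instant relief; the document does not support that.

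A reader might also infer a second contradiction, between total time in 3.2.5.2.7 and 180 minutes in 3.3.3.2.7. The text does not bear this out: 3.3.3.2.7 speaks of a total time of 180 minutes, which reads as the same rule with its value filled in. Section 2.1.1 has the questionnaire completed "during the hypoglycemia induction phase and for up to 180 minutes after treatment with glucagon", which is consistent with that value. Nor can the window in 3.2.2, "Protocol time 120, 150, 180: -15 minute to +15 minute", be used to argue for a spread of censoring times. It assigns categorical values to protocol times, while this endpoint uses actual time. A nominal 180 may differ slightly from the actual last answer, but for very rare subjects that is negligible, and fixed censoring at the planned end of follow-up is acceptable.

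Finally, no shift in the p-value should be claimed. The SAP names no survival test and no distribution of times, so any such figure would rest on inputs from outside the document.

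What remains is that the parenthesis is wrong as written, and an analysis plan should not leave the programmer to work out which half of a sentence to follow.

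**Conclusion.** The point holds as a minor correction. The parenthesis in 3.2.5.2.7 contradicts its own lead words, the next bullet and 3.3.3.2.7.

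The numerical consequence arises only if the parenthesis is coded literally and at least one subject never answers No. It distorts the comparison only if such subjects are unevenly divided between treatments. On those conditions, and with 85 subjects observed on each treatment, the treatment mean moves by 2.1 minutes per unrelieved subject, in the direction that flatters the treatment with more of them. The assumed range of 0 to 2 such subjects is mine; the SAP says only that they are very rare. The primary endpoint does not use this item and is unaffected.

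**What to change.** In the first bullet of 3.2.5.2.7, change No to Yes inside the parenthesis, so that the zero value goes to subjects who never answer Yes. Alternatively, delete the parenthesis, as in 3.2.5.2.6. The first option has the small advantage of keeping the criterion in terms of the Yes/No item itself.

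Either way, subjects who never answer No are then handled only by the second bullet and 3.3.3.2.7: censored in the survival analysis, and footnoted in the descriptive summary. No other rule needs to change.

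The cost is one word, or the removal of three. Data collection, the analysis model and the planned outputs stay as they are.

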3.2.6 Safety Variables

3.2.6.1 Adverse Events (AE)

All observed or volunteered adverse events regardless of treatment group or suspected causal relationship to the study drug will be recorded in the eCRF. This information will be imported directly from the EDC.

For all safety variables, if there is need of protocol time, it will be done based on time of receiving glucagon only.

3.2.6.2 Laboratory safety assessments

Laboratory values (biochemistry and hematology) will be imported via a web portal from a database maintained by the central laboratory.

3.2.6.3 Physical examination and ECG

Physical examination evaluations will be imported directly from EDC. Note that only abnormal ECG values will be reported, and these are reported as a sub category on the Physical examination CRF.

3.2.6.4 Vital signs and body weight

[figure not shown]
Vital sign variables and body weight will be imported directly from EDC.

3.2.6.5 Local Tolerability: Visual Analog Scale (VAS), Injection Site Discomfort and DRAIZE SCALE

Local Tolerability includes the VAS, Injection Site Discomfort and Draize scales. These data will be imported directly from the EDC. The questionnaires used to capture these variables are illustrated briefly below; further details are available in the protocol.

3.2.6.5.1 VAS

VAS is reported using a 100-mm scale.

3.2.6.5.2 Injection Site Discomfort

The following variable is derived based on the questionnaire:

- The first question (1a) will derive a category value for discomfort description.
- Question 1b and 1c will be combined to generate the duration of discomfort:
 - If 1c is answered, then Duration of discomfort = answer in 1c.
 - Otherwise:
 - Duration of discomfort = 0.5 (if less than 1 minute checked)
 - Duration of discomfort = 1.5 (if 1-2 minute checked)

- Duration of discomfort = 4 (if 3-5 minute checked)
- Duration of discomfort = 7.5 (if 6-9 minute checked)

1a. How would you describe any discomfort you felt from the study drug? (Check all that apply):

_____ None (**Please ignore question 1b.**)

_____ Pain (e.g., throbbing, soreness, muscle ache)

_____ Itching

_____ Tingling, twitching or numbness

_____ Irritation (e.g., burning, stinging)

Other or additional comments: _____

1b. About how long did the discomfort last after the injection? (Check one):

_____ Less than 1 minute

_____ 1-2 minutes

_____ 3-5 minutes

_____ 6-9 minutes

_____ at least 10 minutes (**Please complete question 1c before leaving the clinic.**)

1c. In total, how long did the discomfort last after the injection? (Please enter a number below):

_____ Minutes

3.2.6.5.3 Draize (Erythema and or edema)

Erythema and edema formation at the site of injection is assessed using the Draize scale shown below:

Erythema Formation		Edema Formation	
Description	Score	Description	Score
No erythema	0	No edema	0
Very slight erythema Barely perceptible	1	Very slight edema Barely perceptible	1
Well defined erythema	2	Well defined edema	2

Moderate erythema	3	Moderate edema Raised approx. 1 mm	3
Severe erythema Beet redness to slight eschar formation	4	Severe edema Raised more than 1 mm and beyond exposure area	4

3.3 STATISTICAL METHODS

3.3.1 General guideline for descriptive summaries

For continuous variables, mean, standard deviation, minimum, and maximum will be presented for each treatment group.

For categorical variables, count and % of subjects/counts in each treatment group will be presented.

3.3.2 Baseline Characteristics

3.3.2.1 Demographics

The demographics variables of age, sex, race and ethnicity will be presented descriptively.

3.3.2.2 Subject disposition

Subject disposition will be summarized for treatment group, population and study completions.

3.3.2.3 Medical History

Medical History will be summarized by body system.

3.3.2.1 Prior and Concomitant Medications

All Medications will be separated as prior and concomitant medication based on ending date and randomization date. It will be summarized descriptively.

3.3.3 Efficacy Analysis

3.3.3.1 Primary Endpoint analysis

The primary endpoint analysis will be based on the sample mean and SE of (D_{ht} , as defined in section 3.2.5.1). Descriptive summary will be presented for each treatment group.

H0: G-Pen is inferior to control (population mean failure score difference (G-Pen - Control) exceeds 0.1

Ha: not H0

Inferential analysis will be based on the following criterion:

Reject H0, if $D_{ht} + 2.8 SE \leq 0.1$, (Establish non-inferiority)

Where SE is the estimated standard error as defined in section 3.2.5.1

This analysis will be repeated for ITT and PP populations and also time based on both “receiving glucagon” and “decision to dose” time. In total, four groups of summary tables will be presented.

3.3.3.2 Secondary Endpoints

3.3.3.2.1 Binary Responses

The same test as described in previous section 3.2.5.1 will be applied to each of the binary responses defined in section 3.2.5.2.1.

Note that all of these analyses will be repeated for ITT and PP population as well as time based on both “receiving glucagon” and “decision to dose”.

3.3.3.2.2 Number of subjects having glucose >70 mg/dL within 30 minutes of receiving glucagon.

The number of subjects having glucose >70 mg/dL within 30 minutes of receiving glucagon will be presented descriptively.

This will be done in the ITT population only, and will be done for time based on both “receiving glucagon” and “decision to dose”.

Note that subgroup analysis is needed for this (section 3.3.5.1)

3.3.3.2.3 Pharmacodynamics Analyses

All of the PD parameters (as defined in section 3.2.5.2.2) will be presented descriptively.

A mixed model with treatment, period and sequence as fixed factors and subject as a repeated factor will be applied to compare the least square mean differences. Log transformation will be applied if skewness is observed. Unstructured covariance matrix will be used for the covariance matrix unless the model failed. In such case, structured covariance matrix will be selected based on the one given the smallest AIC (Akaike Information).

P-value for the difference test and 90% confidence for non-inferior test will be reported.

Additionally, mean glucose curve from 0 to 180 minutes post receiving glucagon will be presented graphically for each treatment. For this group of figures, the protocol defined time (section 3.2.1) will be used.

The mean glucose curve during hypoglycemia induction time will also be presented for each treatment. Since there is no protocol time for hypoglycemia induction stage, the mean glucose will be summarized for every 5 minutes based on the glucagon injection time.

This will be done based on the ITT population only, and will be done with time based on both “receiving glucagon” and “decision to dose”.

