2.1.3 Randomization

Randomization will be carried out via the Vision™ electronic data capture (EDC) system, version 9.3. Subjects meeting all eligibility criteria and achieving a baseline euglycemic steady state at the first treatment visit as described in the protocol, completing the baseline will be randomized 1:1 by site in simple blocks to receive G-Pen™ glucagon or Lilly glucagon injection at the first treatment visit.

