2.1.4 Unblinding

This is a single-blind study. Only the subjects are blinded for treatment. The investigator and clinical staff will be aware of the treatment. Thus, there is no unbinding needed.

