3.2.5.2.3 Pharmacodynamics (PD) Parameters

The PD endpoints will be derived from the individual glucose profiles. The Baseline Glucose will be the last glucose measurement prior to time 0.

Actual Time will be used to the calculation of the following variables.

If insulin starts after receiving glucagon, the glucose values post insulin start will be censored out and considered as missing.

- Cmax : Maximum concentration of Glucose
- TMax : Time (in mins) when Glucose CMax is reached
- AUC₀₋₃₀: Area under the curve of Glucose from 0 to 30 minutes

- AUC₀₋₃₀ of Glucose will be calculated as the sum of areas of trapezoids, which are composed of adjacent Glucose values. The following rules will be considered:
 - If there are missing data points before the last observed value, they will be imputed as described in section 3.2.1
 - If there are missing data points after the last observed value, they will not be extrapolated and the AUC will be treated as undefined.
- AUC₀₋₁₈₀: Area under the curve of Glucose from 0 to 180 minutes
 - AUC₀₋₁₈₀ of Glucose will be calculated as the sum of areas of trapezoids, which are composed of adjacent Glucose values. The following rules will be considered:
 - If there are missing data points before the last observed value, they will be imputed as described in section 3.2.1.
 - If there are missing data points after the last observed value, they will not be extrapolated and the AUC will be treated as undefined.
- Time for plasma glucose to reach >70.0 mg/dL from receiving of glucagon.
 - The time stamp for 70.0 mg/dL will be imputed using linear interpolation between the two adjacent time points
- Time for plasma glucose to increase by at least 20 mg/dL from receiving of glucagon.
 - The time stamp for 20 mg/dL increase will be imputed using linear interpolation between the two adjacent time points

These PD parameters will be done based on both receiving glucagon and decision to dose.

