4.3 PROTOCOL VIOLATIONS

Potential protocol violations are incorporated into the definition of Per Protocol Population (see 3.1.2). This definition excludes from PP analysis any subject who has one of the following 4 major protocol violations:

1. Fails to meet all eligibility criteria.
2. Fails to meet the definition of hypoglycemia steady state prior to dosing at either treatment visit. A steady state of hypoglycemia is defined as two consecutive plasma glucose values between 43.0 and 49.9 mg/dL, and a linearly extrapolated 8-minute later glucose value \geq 42.0 mg/dL.
3. Fails to complete both treatment visits.
4. Fails to receive a dose of both test articles during the study (G-Pen and Lilly Glucagon).

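### The PD mixed model leaves out pre-dose glucose, which gives up modest precision on time to >70 mg/dL and AUC0-30

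*SAP*

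**What the plan says.** SAP section 3.3.3.2.3 fixes the PD model: "A mixed model with treatment, period and sequence as fixed factors and subject as a repeated factor will be applied". It reports a p-value and a 90% confidence interval, in the ITT population only, on two clocks (from injection and from decision to dose). Section 3.2.5.2.3 defines the starting value: "The Baseline Glucose will be the last glucose measurement prior to time 0". No section enters that value into the model.

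Four other statements bear on the point:

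- Section 4.3 makes pre-dose steady state a per-protocol condition: "two consecutive plasma glucose values between 43.0 and 49.9 mg/dL", with a linearly extrapolated 8-minute value of at least 42.0 mg/dL.
- Section 3.2.2 allows two time zeros: "Protocol time zero will be based on either receiving glucagon or decision to dose". Each period can therefore have two different baselines.
- Section 2.1.3 randomizes subjects on "achieving a baseline euglycemic steady state at the first treatment visit", which is before hypoglycemia is induced.
- Section 2.1.4 says of blinding: "The investigator and clinical staff will be aware of the treatment".

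**The concern.** The design is a "single-blind, two-way crossover efficacy and safety in-patient study", so the treatment contrast is made within subjects and stable differences between subjects drop out. Differences in starting glucose between one subject's two visits do not drop out. They matter most where the endpoint is a fixed threshold or an early area. Within the steady-state window, the rise needed to reach 70 mg/dL runs from 70 - 49.9 = 20.1 to 70 - 43.0 = 27.0 mg/dL, a ratio of 1.34. A 6.9 mg/dL difference in starting value, if it persisted for 30 minutes, would be 6.9 x 30 = 207 mg·min/dL of AUC0-30.

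At stake is the width of the intervals for these secondary PD comparisons. Timing also matters: a baseline covariate is credible if prespecified, but looks selective if added after an imbalance has been seen.

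**Working it through.** **The plan's own figure.** The SAP's only power figure is 88% for the primary failure score with N = 85 (section 2.1.2). Simulating the section 3.3.3.1 rule gives 87.6% with failure rates of 0% on control and 2% on G-Pen and independent 5% missingness in each period. The SAP does not state the control rate; 1% against 3% gives 73%. None of this depends on the PD model. The SAP gives no SD, correlation, margin or power for any PD endpoint, so the results below are ranges under assumptions.

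**Spread of baseline.** The window in section 4.3 is 49.9 - 43.0 = 6.9 mg/dL wide. If baseline is uniform, SD = 6.9/√12 = 1.99 mg/dL. The largest possible SD, with half the values at each end, is 6.9/2 = 3.45.

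**Formula.** Let b be the size of the slope of the outcome on baseline, and take the outcome SD as the total within-subject SD. Then ρ = b x SD(baseline)/SD(outcome), and the variance cut is ρ². One within-subject covariate multiplies the remaining variance by 1 + 1/(f - 2). With 85 complete subjects, f = 85 - 2 = 83, so the factor is 1 + 1/81 = 1.0123. The CI width ratio is √[(1 - ρ²) x 1.0123].

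**Results at SD(baseline) = 1.99 (slopes, rise rates and outcome SDs assumed).**

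| Endpoint | b | Outcome SD | Variance cut ρ² | CI width, net of the 1-df cost |
|---|---|---|---|---|
| Time to >70 mg/dL | 1/rate, rate 1.5-3 mg/dL/min | 3-8 min | 0.7-19.6% | 0.3% wider to 9.8% narrower |
| AUC0-30 | 30 | 200-500 | 1.4-8.9% | 0.1-4.0% narrower |
| Cmax | 1 | 15-40 mg/dL | 0.3-1.8% | 0.5% wider to 0.3% narrower |
| AUC0-180 | 180 | 2500-6000 | 0.4-2.1% | 0.4% wider to 0.4% narrower |
| Time to +20 mg/dL | about 0 | any | about 0 | 0.6% wider |

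Two entries in full:

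- Time to >70, central case (2 mg/dL/min, SD 4 min): ρ = (1.99/2)/4 = 0.249 and ρ² = 6.2%. Net variance ratio: 0.938 x 1.0123 = 0.950, a CI about 2.6% narrower.
- AUC0-30, SD 200: ρ = 30 x 1.99/200 = 0.299 and ρ² = 8.9%. Net variance ratio: 0.911 x 1.0123 = 0.922.

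**Break-even.** (1 - ρ²)(1 + 1/81) = 1 gives ρ² = 1/82, so |ρ| = 0.11. At ρ = 0 the CI is √1.0123 = 1.006 times as wide.

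**Sensitivity.**

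- If a subject's two baselines have correlation r, the within-subject baseline variance, and so ρ², shrinks by the factor (1 - r). At r = 0.5 the central 6.2% becomes 3.1%.
- If the assumed SD is residual rather than total, the top value for time to >70 is 1.76/(9 + 1.76) = 16%, not 20%.
- If the last value ranges uniformly over 42.0-49.9, SD = 7.9/√12 = 2.28, and the top values become 25.7% for time to >70 and 11.7% for AUC0-30.
- At the maximum SD of 3.45, the AUC0-30 variance cut is 4.3-26.8%. Before the 1-df cost, the largest CI gain is still only 2.7% for Cmax and 3.1% for AUC0-180.

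**The case against.** The strongest reply is that nothing in the SAP is wrong. Treatment, period, sequence and subject form the standard model for a two-period crossover, and visit-to-visit baseline variation is already reflected in its standard error. Deriving a baseline does not promise a covariate, because the SAP needs it for another endpoint: "Time for plasma glucose to increase by at least 20 mg/dL from receiving of glucagon". This stands. A reader might infer bias or an internal contradiction, and the documents support neither.

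A reader might also infer that precision comes free on every PD endpoint. It does not. Time to +20 mg/dL already has baseline built in, and for Cmax and AUC0-180 the gain is about 1% of CI width or less before the degree-of-freedom cost and may be a small loss after it.

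A third tempting inference is that the ITT analysis makes the gain much larger, because the 43.0-49.9 rule is only a per-protocol condition. Periods outside the window would indeed raise it. But section 2.1.1 describes induction continuing to a verified stable state before treatment, periods never dosed supply no PD data, and the SAP does not show how many dosed periods fell outside.

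The objection with most practical force concerns which baseline is used. Pre-dose glucose is measured after randomization by unblinded staff. On the injection clock, the last value before time zero can fall inside the preparation time, which section 3.3.3.2.8 itself compares between treatments. Adjusting for such a value could remove part of a treatment effect. Taking the value at or before the decision to dose removes the preparation-time problem but not the lack of blinding.

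**Conclusion.** This is a low-priority improvement, limited to time to >70 mg/dL and AUC0-30. Under the stated assumptions the variance falls by roughly 1-20% (about 6% centrally) for the first and 1-9% for the second. The central 6% is worth about 1/0.938 = 1.066, or 6-7% more subjects, before the degree-of-freedom cost. The low ends are at or near break-even.

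The size rests on a uniform baseline in the 6.9 mg/dL window, uncorrelated baselines within a subject, and rise rates, slopes and outcome SDs that are not in the SAP. The calculation is on the untransformed scale, whereas section 3.3.3.2.3 allows a log transformation. The primary decision and N = 85 do not change.

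**What to change.** In section 3.3.3.2.3, for AUC0-30 and time to >70 mg/dL only, add two covariates to the mixed model: the period-specific last plasma glucose at or before the decision to dose, and the subject's mean of that value over the two periods. Use the same value on both clocks. The subject-mean term ensures that only within-subject baseline differences adjust the treatment contrast. State that for a subject with one period the mean equals the single value. A prespecified sensitivity analysis would be an acceptable lighter version. Leave Cmax, AUC0-180 and time to +20 mg/dL as they are.

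The cost is SAP wording and up to two degrees of freedom, with no new data. If baseline is unrelated to outcome, the CI is about 0.6% wider. The SAP should acknowledge that this baseline is measured after randomization by staff who know the treatment, and the unadjusted result should be shown alongside.
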